	
proportion of Responders in the Test and the Reference product groups is numerically and statistically superior to that of the Placebo ($p < 0.05$; using a two-sided Cochran-Mantel-Haenszel [CMH] test, stratified by clinical site) then superiority of the Test and Reference products over Placebo will be concluded.
 
The same statistical approach will be conducted for analysis of the secondary endpoint in the mITT population.
 
To declare superiority of the Test and Reference products over Placebo, their superiority must be demonstrated for only the primary endpoint in the mITT population.
 
Treatment-by-Site Interaction and Pooling of Clinical Sites
 
As this is a multiple-site study, the interaction of treatment-by-site may be evaluated for the primary efficacy endpoint in the PP population for equivalence testing. The treatment-by-site interaction will be evaluated by the Breslow-Day test for homogeneity of the odds ratio at the 5% significance level ($p < 0.05$, 2-sided). A site(s) with a low enrollment rate(s) may be pooled with its geographically closest site, so as to avoid bias in the stratification of the sites in the CMH test and in the estimation of a treatment-by-site interaction effect. The pooling will be done for low enrolling sites that account for less than 4-7% of the total number of patients in the PP population at the site with the highest enrolling rate in the PP population. If the treatment-by-site interaction term is found to be statistically significant ($p < 0.05$) for the primary endpoint, then the interaction term will also be assessed for clinical relevance before pooling the data across sites. This will include examination of Responder rates at each site where sample sizes per treatment may be influential in the assessment of the interaction.

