8.3 Scientific and Statistical Considerations

8.4 Justification for use of Placebo

A placebo group is included to confirm the sensitivity of the study and minimize the possibility of a false positive result of bioequivalence. Therefore, in addition to demonstrating bioequivalence between Test and Reference products, both active products should show statistical superiority to the Placebo.¹⁴⁻¹⁶

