9.0 STUDY OBJECTIVES

The objectives of this study are to:

1. Evaluate the therapeutic equivalence of a generic Estradiol Vaginal Cream USP, 0.01% (Prasco LLC) to the Reference product, Estrace[®] Cream (Estradiol Vaginal Cream, USP, 0.01%) (Warner Chilcott) in the treatment of VVA.
2. Demonstrate the superiority of the Test and Reference (active) treatments over Placebo (vehicle) treatment in patients with VVA.
3. Compare the safety of Test, Reference and Placebo treatments in patients with VVA.

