11.6 Efficacy Analyses

Primary Endpoint Analysis

Therapeutic Equivalence:

Therapeutic equivalence will be evaluated for both primary and secondary endpoints in the PP population. If the 90% confidence interval (calculated using Yates’ continuity correction) on the absolute difference between the proportion of patients identified as Responders in the Test and Reference groups ($p_T - p_R$) is contained within the range [-20%, +20%] then therapeutic equivalence of the Test product to the Reference product will be considered to have been demonstrated.

The same statistical approach will be conducted for analysis of the secondary endpoint in the PP population.

To declare therapeutic equivalence of the Test product to the Reference product, equivalence must be demonstrated for only the primary endpoints in the PP population.

Superiority to Placebo

Superiority of the Test and Reference products against the Placebo product for the primary endpoint will be evaluated in the mITT population using last observation carried forward (LOCF). If the proportion of Responders in the Test and the Reference product groups is numerically and statistically superior to that of the Placebo ($p < 0.05$; using a two-sided CMH test, stratified by clinical site) then superiority of the Test and Reference products over Placebo will be concluded.

The same statistical approach will be conducted for analysis of the secondary endpoint in the mITT population.

To declare superiority of the Test and Reference products over Placebo, their superiority must be demonstrated for only the primary endpoint in the mITT population.

Treatment-by-Site Interaction and Pooling of Clinical Sites

As this is a multiple-site study, the interaction of treatment-by-site may be evaluated for the primary efficacy endpoint in the PP population for equivalence testing. The treatment-by-site interaction will be evaluated by the Breslow-Day test for homogeneity of the odds ratio at the 5% significance level ($p < 0.05$, 2-sided). A site(s) with a low enrollment rate(s) may be pooled with its geographically closest site, so as to avoid bias in the stratification of the sites in the CMH test and in the estimation of a treatment-by-site interaction effect. The pooling will be done for low enrolling sites that account for less than 4-7% of the total number of patients in the PP population at the site with the highest

CONFIDENTIAL PROTOCOL

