### **8.2 Efficacy Analyses**

#### **8.2.1 Analysis of Primary Efficacy Endpoint**

##### **Therapeutic Bioequivalence Analysis**

Therapeutic equivalence of the Test product to the Reference product based on the primary endpoint will be evaluated in the PP population after the end of treatment on Day  $8 \pm 1$ .

Based on the usual method used in OGD for binary outcomes, the 90% confidence interval for the difference in success proportions between test and reference treatment should be contained within  $[-0.20, +0.20]$  in order to establish equivalence.

The compound hypothesis to be tested is:

versus

where  $\hat{p}_1$  = cure rate of test treatment  
 $\hat{p}_2$  = cure rate of reference treatment.

Let

$n_1$  = sample size of test treatment group  
 $a_1$  = number of cured patients in test treatment group  
 $n_2$  = sample size of reference treatment group  
 $a_2$  = number of cured patients in reference treatment group

, and

The 90% confidence interval for the difference in proportions between test and reference will be calculated as follows, using Yates' correction:

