## STATISTICAL ANALYSIS PLAN

**Estradiol Vaginal Cream USP, 0.01%**

**Protocol/Study Number 71759501**

If the 90% confidence interval (calculated using Yates' continuity correction) for the absolute difference between the proportion of patients considered as "Responders" (at least a 25% reduction from baseline in the sum of % basal/parabasal + % intermediate cells on vaginal cytology AND vaginal pH < 5.0 with a change from baseline vaginal pH of at least 0.5) in the Test and Reference groups is contained within the range [-20%, +20%] then bioequivalence of the Test product to the Reference product will be considered to have been demonstrated for the primary endpoint.

To declare therapeutic equivalence of the Test product to the Reference product, equivalence must be demonstrated for only the primary endpoints in the PP population.

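### The protocol concludes therapeutic equivalence from the per-protocol 90% CI alone; the superiority over Placebo that Protocol 8.4 expects in addition is not part of any visible decision rule

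*Protocol*

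**What the plan says.** **Equivalence rule.** In the Synopsis and in Protocol 11.6, the condition is that the Yates-corrected 90% CI for the Test minus Reference difference in Responder proportions, in the PP population, falls inside [-20%, +20%]. If so, "then therapeutic equivalence of the Test product to the Reference product will be considered to have been demonstrated". A later sentence in both places says that to declare equivalence "equivalence must be demonstrated for only the primary endpoints in the PP population".

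**Superiority rule.** It stands separately: mITT population, LOCF, two-sided CMH test stratified by site, p < 0.05. If Test and Reference both pass, "then superiority of the Test and Reference products over Placebo will be concluded". Protocol 9.0 lists it as its own objective: "Demonstrate the superiority of the Test and Reference (active) treatments over Placebo (vehicle) treatment in patients with VVA".

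**Rationale.** Protocol 8.4 explains the placebo group as a means to confirm sensitivity and to "minimize the possibility of a false positive result of bioequivalence". It continues that, "in addition to demonstrating bioequivalence between Test and Reference products, both active products should show statistical superiority to the Placebo".

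**SAP.** Section 8.2.1 presents the interval as something that should be met "in order to establish equivalence", which is a necessary condition. Its conclusion is by endpoint: equivalence "will be considered to have been demonstrated for the primary endpoint". Section 8.2.2 does the same for the secondary endpoint and calls that analysis supportive. Neither section says what failed superiority would mean for the equivalence claim.

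**The concern.** An equivalence comparison of two actives cannot by itself show that the trial was able to detect an effect. If neither product works in this trial, or the endpoint cannot register an effect after seven days, Test and Reference will look alike and the interval will tend to fall inside the margin. Protocol 8.4 recognises this and names the safeguard, but the if-then sentence in the Synopsis and 11.6 is complete without it.

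At stake is the label on the main conclusion. With the CI criterion met and superiority failed, 11.6 says therapeutic equivalence has been demonstrated, while 8.4 implies that sensitivity was not confirmed. The visible text has no prespecified way to resolve that. The same can happen when Test does no better than vehicle and Reference's advantage over Placebo is smaller than 20 points.

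**Working it through.** **1. Inputs.** The margin (±0.20), the 90% interval with Yates' correction and the two-sided 0.05 CMH test come from Protocol 11.6. Allocation 2:2:1 is from the Synopsis. The total of about 535 is from the title page: 535 × 2/5 = 214 per active arm and 535 × 1/5 = 107 on Placebo. The 535 cannot be reproduced, because its rates, power and retention are not visible; the point does not depend on it. Assumed: responder rates as shown; 60%, 80% or 100% of each active arm in PP (128, 171 or 214); mITT equal to all randomised; one stratum; LOCF not modelled.

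**2. CI rule alone, equal true rates.** The SAP's formula is not legible in the text available, so the usual form is used. With d the observed Test minus Reference difference, the interval is

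d ± { 1.645 × √[pT(1−pT)/nT + pR(1−pR)/nR] + ½(1/nT + 1/nR) }.

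Hand check at 50% in both arms, 128 per arm: SE = √(2 × 0.25/128) = 0.0625, and half-width = 1.645 × 0.0625 + 1/128 = 0.1106. The observed difference may then reach 0.20 − 0.1106 = 0.0894, or 1.43 SE, which gives a pass probability of about 0.85. At 10%, 171 per arm: SE = 0.0324, half-width = 0.0534 + 0.0058 = 0.0592, and the room left is 0.1408, or 4.3 SE, so a pass is almost certain.

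Exact enumeration over all pairs of counts gives the probability that the rule declares equivalence:

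| Responder rate, all arms | 128 per arm | 171 per arm | 214 per arm |
|---|---|---|---|
| 5% | 1.000 | 1.000 | 1.000 |
| 10% | 0.999 | 1.000 | 1.000 |
| 20% | 0.972 | 0.996 | 0.999 |
| 30% | 0.914 | 0.978 | 0.995 |
| 40% | 0.861 | 0.959 | 0.988 |
| 50% | 0.850 | 0.955 | 0.982 |

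**3. Superiority of both actives, equal true rates.** For each active against Placebo, Z = (a − E)/√V. Here a is the number of responders on the active, t the responders in both arms, N = 214 + 107 = 321, E = 214t/N, and V = 214 × 107 × t(N − t)/[N²(N − 1)]. Success is Z > 1.96. The exact chance that both pass is 0.0067 to 0.0081 over 5% to 50%. This is plausible: independent tests would give 0.025² = 0.0006 and identical tests 0.025. The shared Placebo arm gives a correlation of (1/107)/(1/214 + 1/107) = 2/3, so the answer lies between.

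**4. Both rules together, equal true rates** (1,000,000 simulated trials per setting, PP nested in mITT). The CI criterion passes while superiority is not shown for both actives in 0.84 to 0.99 of trials. Neither active is superior in 0.82 to 0.97. With the link, equivalence is declared in about 0.007 to 0.008.

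**5. Test no better than vehicle.** With Test = Placebo = 10% and Reference = 20%, the CI rule passes in 0.67/0.79/0.87 (128/171/214 in PP), against about 0.02 with the link. At 171 per arm, the CI passes without both actives superior in 0.77; that splits into 0.33 with neither active beating Placebo and 0.44 with exactly one. The effect fades at the margin: with Reference at 30%, it is about 0.04 against 0.003 or less.

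**The case against.** **Section 8.4 already states the link, and superiority is an objective with its own test and a place in the sample-size basis.** True. A reader might infer that the plan has dropped the placebo safeguard; it has not. But 8.4 says what should be shown, in a rationale section, while 11.6 states when the conclusion is reached.

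**The CI sentence can be read as endpoint-level.** It sits under a heading for the primary endpoint, and the same approach is then applied to the secondary. This is a fair reading of intent, but the sentence speaks of the Test product's equivalence to the Reference product, without the qualifier that the SAP adds.

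**The word 'only' waives superiority.** A reader might infer this from "equivalence must be demonstrated for only the primary endpoints in the PP population". The documents do not support it: in context the word sets aside the secondary endpoint.

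**The SAP repeats the unconditional rule.** It does not. The unconditional sentence is in the protocol alone; the SAP merely lacks the link.

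**The numbers overstate the problem.** Partly right. With equal arms, the CI-rule probability is simply the power of the equivalence test. With Reference at 20% and Test at 10%, the true difference is inside the margin, so passing is correct under the stated hypothesis and reflects the width of the margin as well as the missing link. The 0.77 must not be read as trials in which neither active beat Placebo; that is 0.33.

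**Hidden text may hold the joint rule.** Protocol 8.3, the sample-size details and the table shells cannot be checked. This limits the point to visible text, but a rule there would still have to be reconciled with the wording of 11.6.

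**Conclusion.** The concern holds in this form: the Synopsis and Protocol 11.6 make the PP interval sufficient for therapeutic equivalence, and no visible decision rule adds the superiority that 8.4 expects. It should be fixed. It is a missing connection between analyses that are already planned, not a missing analysis.

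A reader might infer that a failed Placebo comparison would be concealed. The documents do not support that: it would be reported as a failed objective beside the equivalence result. What is wrong is that the equivalence conclusion would stand unqualified.

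The size rests on assumed responder rates and PP retention and on a single-stratum approximation. The direction does not change over the range tried: where no arm differs, the written rule declares equivalence in at least 0.85 of trials and the joint rule in under 0.01.

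**What to change.** 1. **Synopsis and Protocol 11.6.** End the CI sentence with: *then the equivalence criterion for the primary endpoint will be considered to have been met.*
2. **Synopsis, Protocol 11.6 and SAP 8.2.1.** Replace the sentence on declaring equivalence with: *Therapeutic equivalence will be declared only if (a) the Yates-corrected 90% CI for the Test minus Reference difference in Responder proportions in the PP population lies within [-20%, +20%], and (b) Test and Reference each have a Responder proportion numerically and statistically superior to Placebo in the mITT population with LOCF (CMH stratified by site, two-sided p < 0.05). The secondary endpoint is supportive only.*
3. **SAP 8.2.2.** Replace its sentence on declaring equivalence with a reference to the rule in 8.2.1. The endpoint-level CI sentences in the SAP can stay.

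No new data, test or population is needed. No alpha adjustment is needed either, because every condition must hold, so SAP 8.4 stands. Protocol 11.2 and SAP 5 already say the sample size was estimated for superiority of each active.

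The cost is that success now also depends on both superiority tests. With 171 per active arm in PP and 214/214/107 in mITT, under assumed rates:

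| Actives vs Placebo | CI alone | With the link |
|---|---|---|
| 50% vs 10% | 0.95 | 0.95 |
| 30% vs 10% | 0.98 | 0.96 |
| 25% vs 10% | 0.99 | 0.86 |
| 50% vs 30% | 0.95 | 0.86 |
| 20% vs 10% | 1.00 | 0.51 |

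The loss is large only where active and Placebo are hard to tell apart. The sponsor should check it against its own planning rates and make the change before the treatment codes are released.

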11.7 Safety Analysis

Adverse events will be classified using standard MedDRA terminology Version 20.0 or higher and summarized by treatment group. Summary tables comparing the type, incidence, date of onset, date of resolution, severity, action taken, outcome and Investigator’s opinion of relationship to the study product will be prepared by treatment group. If sufficient data exist, AE frequencies will be compared between treatments using Fisher’s exact test or a similar test.

Signs and symptoms of VVA will not be considered AEs, unless in the Investigator’s opinion, they have increased in frequency and/or severity to such an extent that the Investigator/patient considers that it is in the patient’s best interest to be dropped from continued participation in the study and given alternative therapy for their condition.

Concomitant medication use during the study will be tabulated by patient.

12.0 REGULATORY OBLIGATIONS

12.1 Institutional Review Board

The study protocol, ICF, Investigator’s Brochure, or package insert (as applicable), and any specific advertising will be submitted to, and approved by, an IRB before the start of the study. A form must be signed by the chairman or designee of the IRB noting the approvals. This notification of the board’s approval along with a description by profession and gender of the board’s composition will be provided to the Sponsor.

12.2 Study Documentation

This study will be conducted in compliance with the protocol; Good Clinical Practices and all applicable regulations, including the Federal Food, Drug and Cosmetics Act, US applicable Code of Federal Regulations (title 21), parts 50, 56, 312, 320, and any IRB requirements relative to clinical studies; and the Declaration of Helsinki, June 1964, as modified by the 64th World Medical Association General Assembly, October 2013.^{16,20-22} The Investigator will permit trial-related monitoring, audits, IRB review and regulatory inspections providing direct access to source data/documents.

12.2.1 Protocol

The Investigator indicated on FDA Form 1572 will act as the Principal Investigator at each study site. Protocols will be noted as approved by placement of the [REDACTED] Representative’s signature on the cover page. The Sponsor of the study will also approve the protocol by having a study-responsible individual sign the protocol cover page. The Principal Investigator will sign the protocol signature page indicating their agreement to conduct the study according to the protocol.

CONFIDENTIAL PROTOCOL

A Randomized, Double-Blind, Placebo-Controlled, Parallel-Design, Multiple-Site Study to Evaluate the Therapeutic Equivalence of Estradiol Vaginal Cream, USP, 0.01% (Prasco LLC) to Estrace® Cream (Estradiol Vaginal Cream, USP, 0.01%) (Warner Chilcott) in the Treatment of Vulvar and Vaginal Atrophy, 71759501

12.2.2 Informed Consent

An ICF that includes all of the relevant elements currently required by FDA and local state regulations will be provided to each prospective study patient before enrollment into the study. The type and method of study, tests to be administered, any potential or possible hazards, and the patient's right to withdraw from the study at any time will be explained to the patients by the Investigator or designee. Once the Investigator or designee is assured that an individual candidate understands the implications of participating in this study, the patient will be asked to give consent by signing and dating in the appropriate areas of the ICF. The Investigator or designee will also sign and date the form, along with a staff member who will sign the ICF as a witness to verify that the patient has indeed received information. If any other language is required, translation will be performed by a certified translator. A copy of the ICF will be provided to the patient.

12.2.3 Protocol and Informed Consent Changes

Sponsor approved changes to the protocol or the ICF will be implemented as revisions to the original documents and will require additional review and approval by the IRB. Revisions to the original protocol will be documented in amendments, incorporated as a preface to the new version. Any revision that substantially alters the study design or increases potential risk to the patient requires the patient's consent to continue in the study. The approvals will be processed in accordance with the established IRB procedures. Copies of all protocol and ICF amendments/revisions, along with letters noting IRB approval, will be submitted to the Sponsor.

12.2.4 Source Documents and Electronic Case Report Forms

All patients will be identified by initials, date of birth and a unique patient number. Source documents will be used to record all study-related data. Source document entries will be used to complete electronic case report forms (eCRFs). A set of eCRFs will be completed for each patient randomized in the study. All data and eCRFs will be reviewed, evaluated and signed by the Investigator.

The original source documents and a copy of the corresponding eCRFs will be retained by the Investigator. Patients who terminate early from the study will have the Visit 3 (End of Study) source/eCRF completed.

12.2.5 Drug Accountability

All study product receipt, inventory, dispensing, dosing and reconciliation records will be maintained in compliance with federal regulations. The study product will be dispensed to qualified study patients according to established procedures. At the end of the study (after the database has been locked) all used and unused study product will be returned to Sponsor or designee.

CONFIDENTIAL PROTOCOL

A Randomized, Double-Blind, Placebo-Controlled, Parallel-Design, Multiple-Site Study to Evaluate the Therapeutic Equivalence of Estradiol Vaginal Cream, USP, 0.01% (Prasco LLC) to Estrace[®] Cream (Estradiol Vaginal Cream, USP, 0.01%) (Warner Chilcott) in the Treatment of Vulvar and Vaginal Atrophy, 71759501

12.2.6 Drug Storage

Study product will be stored at controlled room temperature protected from temperatures in excess of 40 °C (104 °F) in a secure place with access by authorized individuals only. The Investigator will be responsible for maintaining accurate records of drug receipt, dispensing, and return. At the end of the study, all partially used and unused study product will be returned to Sponsor's designee.

Retention of Reserve Samples

Each Investigator will randomly remove at least one block of study product and keep for retention. [REDACTED]

[REDACTED]

12.2.7 Pregnancies

If following initiation of study participation, it is subsequently discovered that a study patient is pregnant or may have been pregnant since the initiation of study participation (i.e. since the signing of ICF), the study product will be permanently discontinued. The Principal Investigator or designee must immediately notify the Medical Monitor of this event. Reporting timelines and [REDACTED]/Sponsor contact will be consistent with SAE reporting guidelines (i.e., pregnancies will be reported to the Sponsor [REDACTED] within 24 hours to the contacts listed in section 10.8.2).

Protocol-required procedures for study discontinuation and follow-up must be performed on the patient. Other appropriate pregnancy follow-up procedures should be considered if indicated. All follow-up information regarding the course of the pregnancy, including perinatal and neonatal outcome will be communicated as per the above guidelines. Infants should be followed for a minimum of eight weeks after birth.

